2.4.5.1 Analyses of adverse events

Generalities

The primary focus of AE reporting will be on TEAEs, presented in each observation period. Pre-treatment and post-treatment AEs will be described separately.

If an AE date/time of onset (occurrence, worsening, or becoming serious) is incomplete, an imputation algorithm will be used to classify the AE as pre-treatment, treatment-emergent, or post-treatment. The algorithm for imputing date/time of onset will be conservative and will classify an AE as treatment-emergent unless there is definitive information to determine it is pre-treatment or post-treatment. Details on classification of AEs with missing or partial onset dates are provided in [Section 2.5.3](#).

AE incidence tables will present, the number (n) and percentage (%) of patients experiencing an AE by SOC, HLGT (when applicable), HLT (when applicable), and PT. Multiple occurrences of the same event in the same patient will be counted only once in the tables within a treatment phase. The denominator for computation of percentages is the safety population within each treatment group.

Sorting within tables ensures the same presentation for the set of all AEs within the observation period (pre-treatment, TEAE, and post-treatment). For that purpose, the table of all TEAEs presented by SOC and PT sorted by the internationally agreed SOC order and decreasing frequency of PTs within SOCs (in the alirocumab 150mg Q4W group) will define the presentation order for all other tables by SOC and PT, unless otherwise specified. The tables of AEs by SOC, HLT, HLT and PT will be sorted by the SOC internationally agreed order and the other levels (HLT, HLT, PT) will be presented in alphabetical order, unless otherwise specified

Analysis of all treatment-emergent adverse events

The following TEAEs summaries will be generated.

- Overview of TEAEs, summarizing number (%) of patients with any
 - TEAE;
 - Serious TEAE;
 - TEAE leading to death;
 - TEAE leading to permanent treatment discontinuation.
- All TEAEs by primary SOC, HLT, HLT, and PT;
- Number (%) of patients experiencing common TEAE(s) presented by primary SOC, HLT and PT (HLT incidence $\geq 2\%$ in any treatment group), sorted by SOC internationally agreed order and by alphabetic order for the other levels (HLT and PT);
- All TEAEs by primary SOC and PT, sorted by the internationally agreed SOC order and by decreasing incidence of PTs within each SOC (in the alirocumab 150 mg Q4W group). This sorting order will be applied to all other tables by SOC and PT of TEAEs, unless otherwise specified;
- All TEAEs by treatment group regardless of relationship in one column and, in the same table a second column with TEAEs related to alirocumab according to investigator's opinion by primary SOC, HLT, HLT and PT;
- All TEAEs by maximal intensity (ie, mild, moderate or severe), presented by primary SOC and PT, sorted by the sorting order defined above;

Analysis of all treatment emergent serious adverse event(s)

- All serious TEAEs by primary SOC, HLT, HLT, and PT;
- All serious TEAEs by treatment group regardless of relationship in one column and, in the same table a second column with TEAEs related to alirocumab according to investigator's opinion, by primary SOC, HLT, HLT, and PT;

Analysis of all TEAE(s) leading to treatment discontinuation

- All TEAEs leading to treatment discontinuation, by primary SOC, HLT, HLT, and PT

Analysis of groupings of adverse events including selected adverse events of special interest

- All grouping of TEAEs including adverse events of special interest as listed in [Section 2.1.4.1](#)(except Pregnancy and overdose with NIMP) will be analyzed using selections defined in [Section 2.1.4.1](#) and will be presented by SMQ and PT (when selection is based on SMQs) and by SOC and PT (when selection is based on the e-CRF tick box or HLT/HGT). The summaries will be sorted by decreasing incidence of PT within each SOC/SMQ (in the alirocumab 150 mg Q4W group).
- [REDACTED]
- Analyses of grouping of AEs for diabetes ([Section 2.1.4.1](#)) will be performed overall and according to the diabetic status at baseline ([Section 2.1.1](#)).

In addition, the following variables will be tabulated for the local injection site reactions TEAEs:

- Intensity of the event (mild, moderate, severe);
- Number of events divided by the number of double-blind IMP injections received (number of open-label IMP injections for analysis in OLTP, number of alirocumab IMP injections for analysis in alirocumab exposed period);
- Time from first double-blind IMP injection to first injection site reaction (time from first open-label IMP injection for analysis in OLTP, from first alircumab injection for analysis in alirocumab exposed period);

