1 FLOW CHARTS

1.1 GRAPHICAL STUDY DESIGN

a: As a general rule, patients start the Run-in period to reach at stable daily dose of atorvastatin 5 mg or non-statin LMTs.

b: When patients have received atorvastatin 5 mg/day or non-statin LMTs at stable daily dose for at least 4 weeks, they can skip the Run-in period and start the study from the Screening period.

c: In order to keep the double-blind manner, injections of placebo will be conducted at W2, W6 and W10.

d: Up-titration to Alirocumab 150 mg Q2W at W24 is done only if LDL-C is ≥ 100 mg/dL or ≥ 120 mg/dL at W20 depending on risk category.

e: Phone Call Visit (PCV).

f: Last administration of up-titrated Alirocumab 150 mg Q2W at W62.

g: The permitted atorvastatin at a dose of 5 mg daily, non-statin LMTs, or diet therapy should remain stable (including dose) throughout the study duration barring exceptional circumstances.

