There was no safety signal in patients who had at least 2 consecutive values of LDL-C <25 or 15 mg/dL (0.65 or 0.39 mmol/L), particularly in regard to neurological or other adverse effects that could potentially be related to low LDL-C (32). The analysis of the safety data with Q2W dosing did not suggest a safety signal as of 31 December 2014.

Overall, the safety profile of the alirocumab Q4W dosing regimen was similar to alirocumab Q2W regimen, except for the frequency and onset of injection site reactions. The reactions tended to occur sooner after the first drug injection, and last longer, in the alirocumab group.

Further details on alirocumab are provided in the Investigator's Brochure.

Rationale for selection of doses / dose regimens in this study:

This study will explore the alirocumab 150 mg Q4W regimen, which represents a potentially viable alternative to a Q2W regimen for some patients.

Statins increases the activity of nuclear translocation of sterol regulatory element-binding protein 2 (SREBP-2), a transcription factor that activates both the LDL-R and PCSK9 genes. It is proposed that a statin-stimulated increased production of PCSK9 may affect the duration of action of alirocumab in the setting of Q4W dosing, because higher rates of PCSK9 production may result in greater target-mediated clearance of the antibody (33). Compared to statins, fibrates and ezetimibe appear to have less effect on PCSK9 levels (34), and a Q4W dosing regimen is expected to maintain sufficient LDL-C lowering throughout the interdosing interval in patients not receiving a statin but receiving these lipid-lowering therapies as well as for alirocumab monotherapy. The addition of a PCSK9 inhibitor to fibrate therapy may achieve beneficial cholesterol lowering along with the other desirable effects of fibrates (e.g., TG reduction) (35).

For patients receiving alirocumab in monotherapy, phase 1 data consistently suggested that the dose of 150 mg given Q4W should also maintain sufficient LDL-C lowering throughout the interdosing interval; similar profile was observed with a background therapy of ezetimibe or fenofibrate, without statin from PKD12910 study.

[REDACTED]

[REDACTED]

[REDACTED]

[REDACTED]

Rationale for protocol design:

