8.1.2 Timing of administration

Screening period (from Week -3 to Week 0): Training Injection

During the screening period, a training injection is planned on Week -1 with a placebo for alirocumab. If needed, a second training injection is authorized before the randomization visit. It is noted that further training with the scheduled double-blind / open-label IMP can be done at any time during the study as necessary.

Double-blind treatment period (from Week 0 to Week 12):

During the double-blind treatment period, patients will be randomized to receive:

- Alirocumab 150mg Q4W alternating with placebo for alirocumab Q4W
OR
- Alirocumab 150 mg Q2W
OR
- Placebo for alirocumab Q2W.

Alirocumab will be administered at Week 0, Week2, Week 4, Week 6, Week 8, and Week 10 (Q2W), or at Week 0, Week 4, and Week 8 with alternating placebo for alirocumab administration at Week 2, Week 6, and Week 10 (Q4W). The first IMP administration at Week 0 will start as soon as possible after the call for randomization using the treatment kit number provided by the IWRS. Patients will be monitored at the study site for at least 30 minutes after the first IMP administration.

All IMP injections will be conducted at the study site under direct site staff supervision after all study assessments have been performed and all laboratory samples have been collected.

Open-label treatment period (from Week 12 to Week 64):

All patients will receive alirocumab 150 mg Q4W from the beginning of the OLTP (Week 12). At the beginning of the OLTP, all patients will be monitored at the study site for at least 30 minutes after the first IMP administration.

At Week 24, the up-titration to alirocumab 150 mg Q2W will be conducted through interactive Web Response System (IWRS) under the following circumstances:

- In patients with heFH or in patients with non-FH with documented CHD, LDL-C is ≥ 100 mg/dL (2.59 mmol/L) at Week 20.
- In patients with non-FH classified as primary prevention category III, LDL-C is ≥ 120 mg/dL (3.10 mmol/L) at Week 20.

In patients with alirocumab 150 mg Q4W, the last injection will be conducted at Week 60. In patients with up-titrated alirocumab 150 mg Q2W, the last injection will be conducted at Week 62.

All IMP injections can be conducted home if patients are able to perform (See [Section 10.1.4](#) and [Section 10.1.4.4](#)).

Throughout the entire study duration:

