2.1.4.1 Adverse events variables

AEs (including SAEs and AESI) are recorded from the time of signed informed consent until the end of the study. All AEs diagnosed by the Investigator, irrespective of the result of the adjudication for CV events, will be reported and described.

All AEs will be coded to a lower-level term (LLT), preferred term (PT), high-level term (HLT), high-level group term (HLGT), and associated primary system organ class (SOC) using the version of Medical Dictionary for Regulatory Activities (MedDRA) currently in effect at Sanofi at the time of the database lock for the first step analysis.

Adverse event observation period

- Pre-treatment AEs are AEs that developed or worsened or became serious during the pre-treatment period.
- Double-blind TEAEs are AEs that developed or worsened or became serious during the double-blind TEAE period.
- Double-blind post-treatment AEs are AEs that developed or worsened or became serious during the double-blind post-treatment period.
- Open-label TEAEs are AEs developed or worsened or became serious during the open-label TEAE period.
- Open-label post-treatment AEs are AEs that developed or worsened or became serious during the open-label post-treatment period.
- Alirocumab exposed TEAEs are AEs developed or worsened or became serious during the alirocumab exposed TEAE period.

AESI include the following AEs:

AESIs are AEs (serious or non-serious) that need to be monitored, documented, and managed in a pre-specified manner described in the protocol. In this study, AESIs are the following (their complete descriptions are provided in the protocol):

- Local injection site reactions, selected using e-CRF specific tick box on the AE page;
- Allergic events:
 - General allergic events will be tabulated. Events will be selected using standardized MedDRA query (SMQ) "hypersensitivity" (broad and narrow) excluding the following preferred terms linked to local injection site reactions ("infusion site dermatitis", "infusion site hypersensitivity", "infusion site rash", "infusion site urticaria", "injection site dermatitis", "injection site hypersensitivity", "injection site rash", "injection site urticaria" and "injection site vasculitis");

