2.4.3.1 Extent of investigational medicinal product exposure

Injection (alirocumab or placebo)

Double-blind IMP injections are those administered from randomization to completion or discontinuation of the double-blind study treatment. These injections contain:

- placebo Q2W for patients randomized in the Placebo Q2W group,
- placebo Q4W (to maintain the blind) or 150 mg Q4W of alirocumab for patients randomized in the Alirocumab 150 mg Q4W group.

- 150 mg Q2W of alirocumab for patients randomized in the Alirocumab 150 mg Q2W group.

The total exposure during the DBTP will be assessed using descriptive statistics for:

- Duration of double-blind IMP injection exposure in weeks defined as: (date of last dose of double-blind IMP injection +14 – date of first dose of double-blind IMP injection) / 7, regardless of intermittent discontinuations (see [Section 2.5.3](#) for calculation in case of missing or incomplete data). Non-integer values will be rounded to 1 decimal place;
- The total number of double-blind IMP injections by patient.

Duration of double-blind IMP injection exposure will be summarized using number, mean, SD, median, minimum and maximum. In addition, it will be summarized according to the following categories: ≥ 1 day and < 4 weeks, ≥ 4 weeks and < 8 weeks, ≥ 8 weeks and < 10 weeks, ≥ 10 weeks.

The total exposure during the OLTP will be assessed using descriptive statistics for:

- Duration of open-label IMP injection exposure in weeks defined as: (date of last dose of open-label IMP injection +14 – date of first dose of open-label IMP injection) / 7, regardless of intermittent discontinuations (see [Section 2.5.3](#) for calculation in case of missing or incomplete data). Non-integer values will be rounded to one decimal place;
- The total number of open-label IMP injections by patient.

Duration of open-label IMP injection exposure will be summarized using number, mean, SD, median, minimum and maximum. In addition, it will be summarized according to the following categories: ≥ 1 day and < 12 weeks, ≥ 12 weeks and < 24 weeks, ≥ 24 weeks and < 36 weeks, ≥ 36 weeks and < 48 weeks, ≥ 48 weeks.

The total exposure during alirocumab exposed period (defined in [Section 2.4.5](#)) for first step analysis only will be assessed using descriptive statistics for:

- Duration of alirocumab IMP injection exposure in weeks defined as:

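### The Q4W injection-site-reaction rate per double-blind injection averages active and blinding placebo injections, so it is not a rate per alirocumab injection; the alirocumab-exposed rate needs a matching numerator

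*SAP*

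**What the plan says.** SAP 2.4.5.1 tabulates, for treatment-emergent local injection-site reactions, the "Number of events divided by the number of double-blind IMP injections received". For other periods it substitutes open-label injections, or the "number of alirocumab IMP injections for analysis in alirocumab exposed period".

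SAP 2.4.3.1 states what the double-blind injections contain: "placebo Q4W (to maintain the blind) or 150 mg Q4W of alirocumab for patients randomized in the Alirocumab 150 mg Q4W group". Protocol 8.1.2 gives active doses at Weeks 0, 4 and 8 and placebo at Weeks 2, 6 and 10 in that arm, against six active doses in the Q2W arm. Protocol 1.1 gives the reason for the placebo doses: "In order to keep the double-blind manner, injections of placebo will be conducted at W2, W6 and W10".

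The events are defined in SAP 2.1.4.1 as "Local injection site reactions, selected using e-CRF specific tick box on the AE page", without reference to what the preceding injection contained. No split by active or placebo injection appears in the visible text. One item in the adverse-event groupings of SAP 2.4.5.1 is blacked out and cannot be judged.

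**The concern.** A rate per injection is normally read as the reactivity of the product injected. In the Q4W arm half of the planned denominator is placebo that exists only for blinding, and open-label Q4W dosing has no such injections. A reader who takes the double-blind figure as the reaction rate for alirocumab 150 mg given Q4W will read it too low if alirocumab injections cause more reactions than placebo. The same reader may then see an apparent rise on entry to the open-label period with no true change.

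Tolerability of each regimen is a secondary objective (Protocol 5.2). Protocol 4 describes the safety of Q4W and Q2W dosing as similar "except for the frequency and onset of injection site reactions", so this is the safety table where a reader will look for a difference between regimens.

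The alirocumab-exposed analysis has a separate problem. For patients randomized to Q4W, its window starts at the first double-blind dose (SAP 2.1.4), so it contains their Week 2, 6 and 10 placebo injections. If the denominator leaves these out while reactions to them are counted, numerator and denominator do not match.

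**Working it through.** The documents give no reaction rate per injection, so there is no stated figure to reproduce.

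**Inputs**
- Planned double-blind injections: Q4W 3 active + 3 placebo; Q2W 6 active; placebo arm 6 placebo (Protocol 8.1.2).
- 53 patients per arm (Protocol 6), so 53 × 6 = 318 planned injections per arm.
- a and p: reactions per active and per placebo injection. Their ratio is an assumption. The nearest figures are 6.2% of alirocumab patients and 4.2% of control patients in the pooled data (Protocol 4). These are patient-level, and using them per injection is assumed: p/a = 4.2/6.2 = 0.68.

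**Double-blind period, rate as specified**
- Q4W: (3a + 3p)/6 = (a + p)/2
- Q2W: 6a/6 = a
- Placebo arm: 6p/6 = p
- Q4W/Q2W = (1 + p/a)/2

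| p/a (assumed) | Q4W/Q2W |
|---|---|
| 1.25 | 1.13 |
| 1.00 | 1.00 |
| 0.68 | 0.84 |
| 0.50 | 0.75 |
| 0.33 | 0.67 |
| 0.20 | 0.60 |
| 0 | 0.50 |

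Illustration with a = 6.2% and p = 4.2% per injection (assumed):
- Q4W: 53 × 3 × (0.062 + 0.042) = 16.5 events, or 5.2% per injection.
- Q2W: 318 × 0.062 = 19.7 events, or 6.2%.
- Placebo: 318 × 0.042 = 13.4 events, or 4.2%.
- Open-label, all injections active: a = 6.2%. The step from 5.2% to 6.2% would be an artefact of injection content.

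**Possible repairs of the double-blind rate**
- Denominator alone changed to active injections: (3a + 3p)/3 = a + p. The ratio to Q2W becomes 1 + p/a, which is 1.68 at p/a = 0.68 and 2.00 at p = a. This over-corrects against Q4W.
- Numerator and denominator split together: Q4W active = 3a/3 = a, ratio to Q2W 1.00; Q4W placebo = 3p/3 = p.

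**Alirocumab-exposed period, if the denominator means active injections**
- Planned active injections before Week 24, including open-label doses at Weeks 12, 16 and 20: Q4W 3 + 3 = 6; Q2W 6 + 3 = 9; former placebo 3. With equal arms the total is 18.
- Q4W placebo injections inside the window: 3.
- Overall rate = (18a + 3p)/18 = a + p/6.
- Relative to a: 1 + 0.68/6 = 1.11, about 11% too high.

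**The case against.** A reader might infer that the definition makes Q4W look better tolerated by construction, or that any gap it shows is not real. The documents support neither. Every arm has six planned double-blind injections, and reactions to placebo injections are in the numerator as well as the denominator. On planned injections the rate is therefore events per patient divided by six in each arm. It shows no difference when p = a and goes against Q4W when p exceeds a. Where Q4W does come out lower, the ratio equals the true ratio of reactions per patient over 12 weeks as dosed, which is a fair randomized comparison.

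A reader might also infer that the exposed-period mismatch distorts the comparison of regimens. It does not, because SAP 2.4.5 presents that period for overall patients, not by arm. The mismatch is also conditional. The SAP does not define its term for alirocumab injections, although the alirocumab safety population in SAP 2.3.6, defined by receipt of alirocumab, makes active injections the plain reading.

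Safety summaries are descriptive, and patient-level incidence, intensity and time to first reaction are reported alongside. These limit the weight of the point, but none of them separates reactions by what was injected. What remains is that the pooled figure describes the blinded Q4W arm, whereas a reader will want the rate for alirocumab as given open-label.

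**Conclusion.** The point holds as one of interpretation and definition. The double-blind Q4W rate is valid per blinded injection. It understates the rate per active injection if active injections cause more reactions than placebo: by 16% at p/a = 0.68, by 50% at the limit, and not at all if p = a. It cannot be set beside the open-label rate. The exposed-period rate is about 11% too high at p/a = 0.68, provided the denominator means active injections and planned dosing is followed.

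Both sizes rest on a patient-level ratio assumed to apply per injection; the documents give no per-injection rates. Protocol 4 makes a > p plausible but does not establish it. Because the output is descriptive and the as-dosed comparison stands, the severity is minor.

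**What to change.** In SAP 2.4.5.1:

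1. Keep the pooled double-blind rate and label it as per blinded injection.
2. Add the rate by content of the most recent injection (Q4W active, Q4W placebo, Q2W active, placebo arm), splitting events and injections together.
3. For the alirocumab-exposed period, define the denominator as active alirocumab injections and count only reactions whose most recent injection was alirocumab.

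The cost is one additional table after unblinding. Each double-blind kit holds a single autoinjector (Protocol 8.5), and treatment numbers and administration dates are source data (Protocol 10.2), so no new data are needed.

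There are two downsides. A written attribution rule is required; most recent injection is the simplest. Also, Q4W active injections are numbers 1, 3 and 5 while Q2W active injections are numbers 1 to 6. If reactions cluster early, as Protocol 4 suggests, the active-to-active comparison is affected by injection order, so the split should be shown or read by injection number.

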2.4.5.2 Deaths

The following summaries of deaths will be generated for the DBTP and the OLTP.

- Number (%) of patients who died by period (on-study, on-treatment, post-study) and reasons for death as adjudicated by the CEC;
- Deaths in nonrandomized patients or randomized but not treated patients
- TEAEs leading to death (death as an outcome on the AE as reported by the Investigator) by primary SOC, HLT, and PT sorted by internationally agreed SOC order, with HLT, and PT presented in alphabetical order within each SOC. TEAE leading to

death are TEAE that led to death regardless of timing of death in relation to IMP injection (ie, death occurring in the TEAE period or during the post-treatment period).

2.4.5.3 Analyses of laboratory variables

The summary statistics (including number, mean, median, Q1, Q3, SD, minimum and maximum) of all laboratory variables (central laboratory values and changes from baseline) will be calculated for each visit or study assessment (baseline, each post-baseline value of the treatment period, last on-treatment and worst on-treatment value) by treatment group. In addition, for some parameters of interest, mean changes from baseline with the corresponding SE could be plotted over time (at same time points) in each treatment group. This section will be organized by biological function as specified in [Section 2.1.4.3](#). For glucose, only fasting samples will be summarized.

The incidence of PCSAs (list provided in [Appendix A](#)), as well as ALT increase as defined as AESI and hemoglobin decrease from baseline $\geq 15\text{g/L}$ (see [Section 2.1.4.1](#)), at any time during the TEAE period will be summarized by biological function and treatment group irrespective of the baseline level and/or baseline level and/or according to the following baseline status categories:

- Normal/missing
- Abnormal according to PCSA criterion or criteria

Glucose (quantitative summary and PCSA) will also be analyzed, overall and according to the diabetes status at baseline defined in [Section 2.1.1](#).

CPK (PCSA) will also be analyzed, overall and according to prior history of side effects caused by statin.

For parameters for which no PCSA criteria are defined, similar table(s) using the normal range will be provided.

Hepatitis C

Analysis of hepatitis C will be done for patients below according to analysis period.

- DBTP (Hepatitis C planned to be tested for patients who prematurely discontinue study treatment during DBTP) in safety population.
- Alirocumab exposed period (at first step analysis only) (Hepatitis C planned to be tested for patients who prematurely discontinue study treatment during alirocumab exposed period) in alirocumab safety population.
- OLTP: in OLT population.

The number and percentage of patients with a post-baseline seroconversion for hepatitis C test will be provided by treatment group in post-baseline (including the TEAE and post TEAE periods) as well as in the TEAE period alone. Post-baseline seroconversion is defined for patients with a negative baseline status who had either a “positive ribonucleic acid” (RNA) or a “confirmed

positive antibody (Ab) with negative RNA” post-baseline status as defined in the table below. Other situations require case by case evaluation and will be described individually if relevant.

The status as regards to hepatitis C virus (HCV) for a patient will be defined as follows for all evaluations (baseline and post-baseline).

Table 1 - Definition of the patient status regarding hepatitis C virus

| Antibody test result | Hepatitis C | | | | |
|--|---------------------------------------|------------------|-----------------------------------|------------------|--------------------------------|
| | Negative | | Positive | | |
| Reflexive test ^a – hepatitis C RNA test | Not available or HCV RNA not detected | HCV RNA detected | HCV RNA not detected ^b | HCV RNA detected | Not available |
| Hepatitis C status - label | Negative | Positive RNA | Negative ^b | Positive RNA | Positive Ab – no RNA available |

^a Test performed at the same time or after the antibody test in the pre-treatment period (for baseline evaluation), or post-baseline, respectively

^b For post-baseline evaluation, a second antibody test with a different type of assay is to be done at the same date or after the first antibody test. The result of this test will modify the final hepatitis C status of the patient in some cases (see details in the text below the table)

The baseline evaluation will be based on tests performed during the pre-treatment period.

In case of multiple hepatitis C tests available for the post-baseline evaluation, the positive status of the patient will be defined as follows:

- “Positive RNA” status if at least one post-baseline positive RNA is detected, regardless of status of the patient at the end of treatment.
- Else “Positive Ab – no RNA available” status if no post-baseline reflexive RNA test is available for at least one post-baseline positive antibody test.

If no antibody test is available or with “indeterminate” as result pre-treatment or post-baseline, respectively, the RNA test (if available) will be used alone to determine the status of the patient. If no RNA is available then the hepatitis C status of the patient will be missing.

The post-baseline status “confirmed positive antibody with negative RNA” will replace “Negative” status as defined above in the case where no RNA was detected post-baseline and the 2 antibody tests surrounding the same visit (from 2 different types of assay) are positive.

For a conservative approach, the post-baseline status “Positive Ab – no RNA available” will not be modified by the availability of a second antibody test from a different assay.

For the description of the positive hepatitis C virus test during the TEAE period, all above rules applied by replacing post-baseline by TEAE period.

Drug-induced liver injury

The liver function tests, namely AST, ALT, ALP, and total bilirubin, are used to assess possible drug-induced liver toxicity. The proportion of patients with PCSA values or ALT increase as

defined in AESI section (see [Section 2.1.4.1](#)) during TEAE period by baseline status will be displayed by treatment group for each parameter.

An evaluation of drug-induced serious hepatotoxicity (eDISH) with the graph of distribution of peak values of ALT versus peak values of total bilirubin will also be presented using post-baseline values during TEAE period. Note that the ALT and total bilirubin values are presented on a logarithmic scale. The graph will be divided into 4 quadrants with a vertical line corresponding to 3 x ULN for ALT and a horizontal line corresponding to 2 x ULN for total bilirubin.

Listing of possible Hy's law cases identified by treatment group (ie, patients with any elevated ALT >3 x ULN, and associated with an increase in bilirubin >2 x ULN, concomitantly or not) with ALT, AST, ALP, total bilirubin, and if available, direct and indirect bilirubin will be provided.

The incidence of liver-related TEAEs will be summarized by treatment group. The selection of PTs will be based on SMQ Hepatic disorder (see [Section 2.4.5.1](#)).

Analysis of clinical laboratory variables in the open-label treatment period

For OLTP, summary tables as described for the DBTP above will be used with the following exception:

- Analyses by visit (unless data warrants further investigation)

Analysis of clinical laboratory variables in the alirocumab exposed period (first step analysis only)

For alirocumab exposed period, summary tables as described for the DBTP above will be used with the following exception:

- Analyses by visit (unless data warrants further investigation)

